6.5.1. Sasanlimab Dose Modifications

No dose reductions are permitted, but the next dosing of sasanlimab may be delayed or skipped for the cycle based on persisting toxicity (see Table 11).

Events, including but not limited to, pneumonitis, colitis, creatinine, and LFT elevation, should be monitored carefully with this class of agents.

Table 11. Sasanlimab Recommended Treatment Modifications for Drug-Related Toxicity (Excluding irAEs)

Hematologic toxicities	
Grade 1 and Grade 2	
 Continue as per schedule.

 Anemia Grade ≥ 3 (hemoglobin < 8 g/dL) 	
 Hold sasanlimab and monitor weekly until resolution to Grade ≤ 1 or baseline. Resume sasanlimab at the next scheduled dose after recovery to Grade ≤ 1 or baseline. Permanently discontinue sasanlimab if anemia does not resolve to Grade ≤ 1 or baseline within 12 weeks or if the same Grade 3 toxicity recurs.

 Neutropenia Grade ≥ 3 (ANC $< 1000/\mu\text{L}$) 	
 Hold sasanlimab and monitor weekly until resolution to Grade ≤ 1 or baseline. Resume sasanlimab at the next scheduled dose after recovery to Grade ≤ 1 or baseline. Permanently discontinue sasanlimab if neutropenia does not resolve to Grade ≤ 1 or baseline within 12 weeks or if the same Grade 3 toxicity recurs.

 Thrombocytopenia Grade ≥ 3 (platelets $< 50,000/\mu\text{L}$) 	
 Hold sasanlimab and monitor weekly until resolution to Grade ≤ 1 or baseline. Resume sasanlimab at the next scheduled dose after recovery to Grade ≤ 1 or baseline. Permanently discontinue sasanlimab if thrombocytopenia does not resolve to Grade ≤ 1 or baseline within 12 weeks or if the same Grade 3 toxicity recurs.
Nonhematologic toxicities	
Grade 1 and Grade 2	
 Continue as per schedule.
Grade 3	
 Hold sasanlimab. Resume sasanlimab at the next scheduled dose after recovery to Grade ≤ 1 or baseline. Permanently discontinue if toxicity does not resolve to Grade ≤ 1 or baseline within 12 weeks or if the same Grade 3 toxicity recurs. Exceptions are: laboratory values that do not have any clinical correlate. For suspected immune-related toxicity follow guidance in Section 10.3.5.
Grade 4	
 Permanently discontinue sasanlimab. Exceptions are: laboratory values that do not have any clinical correlate. For suspected immune-related toxicity follow guidance in Section 10.3.5.

090177e198aafefApproved\Approved On: 22-Nov-2021 20:52 (GMT)

To facilitate the early recognition and prompt intervention in the event of clinically meaningful sasanlimab immune-related AEs, management algorithms have been developed for suspected pulmonary, GI, liver, endocrine, skin, neurological and renal toxicities (see [Appendix 3 Section 10.3.5](#)).

Selected toxicities that do not resolve or worsen following supportive care and dose modifications and with a clinical presentation consistent with a potential irAE without a clear alternative explanation, may require treatment with corticosteroids or other immunosuppressants and should be managed according to the management of irAEs as described in [Appendix 3 Section 10.3.5](#).

6.5.2. Dose Reductions

No dose reductions are permitted for sasanlimab.

Following dosing interruption or cycle delay due to treatment-related toxicity, the PF-07265028 dose may need to be reduced when treatment is resumed.

No specific dose adjustments are recommended for Grade 1 or 2 treatment-related toxicity. However, investigators should always manage their participants according to their medical judgment based on the particular clinical circumstances.

Participants experiencing recurrent and intolerable treatment-related Grade 2 toxicity may resume dosing at the next lower dose level once recovery to Grade ≤ 1 or baseline is achieved.

Dose reduction of PF-07265028 by 1 and, if needed, 2 dose levels will be allowed depending on the type and severity of toxicity encountered. Participants requiring more than 2 dose reductions will be discontinued from the treatment and entered into the Follow-up phase, unless otherwise agreed between the investigator and the sponsor. All dose modifications/adjustments must be clearly documented in the participant's source notes and CRF.

Once a dose has been reduced for a given participant, all subsequent cycles should be administered at the reduced dose level, unless further dose reduction is required. Intraparticipant dose re-escalation is not allowed.

Participants experiencing a DLT may resume dosing at the next lower dose level (if applicable) once adequate recovery is achieved, and in the opinion of the investigator and sponsor, the participant is benefiting from therapy.

6.5.3. Dosing Interruptions

Appropriate follow-up assessments should be done until adequate recovery occurs as assessed by the investigator. Criteria required before treatment can resume are described in the Dose Delays ([Section 6.5.4](#)).

Doses may be held up to 4 weeks until toxicity resolution for PF-07265028 and held up to 8 weeks for sasanlimab. Depending on when the AE resolved, a treatment interruption may lead to the participant missing all subsequent planned doses within that same cycle or even to delay the initiation of the subsequent cycle.

If the AE that led to the treatment interruption recovers within the same cycle, then redosing with PF-07265028 in that cycle is allowed. Doses omitted for toxicity are not replaced within the same cycle. The need for a dose reduction at the time of treatment resumption should be based on the criteria defined in the Dose Reductions [Section 6.5.2](#), unless expressly agreed otherwise following discussion between the investigator and the sponsor. If a dose reduction is applied in the same cycle, the participant may need to return to the clinic to receive new drug supply.

In the event of a treatment interruption for reasons other than treatment-related toxicity (eg, elective surgery) lasting >4 weeks, treatment resumption will be decided in consultation with the sponsor.

6.5.4. Dose Delays

Retreatment following treatment interruption for treatment-related toxicity or at the start of any new cycle may not occur until all of the following parameters have been met:

- ANC $\geq 1,000/\text{mm}^3$.
- Platelets count $\geq 50,000/\text{mm}^3$.
- Hemoglobin ≥ 10 g/dL.
- Nonhematologic toxicities have returned to baseline or Grade ≤ 1 severity (or, at the investigator's discretion, Grade ≤ 2 if not considered a safety risk for the participant).

If a treatment delay results from worsening of hematologic or biochemical parameters, the frequency of relevant blood tests should be increased as clinically indicated.

If these conditions are met within 4 weeks of treatment interruption, PF-07265028 may be resumed. Refer to the Dose Reductions ([Section 6.5.2](#)) for AEs requiring dose reduction at the time of treatment resumption.

If participants require discontinuation of PF-07265028 for more than 4 weeks at any time during the study, then study treatment should be permanently discontinued, unless the investigator's benefit/risk assessment suggests otherwise after discussion with the sponsor. If participants require discontinuation of sasanlimab for more than 8 weeks at any time during the study, then study treatment should be permanently discontinued.

If a treatment interruption continues beyond Day 28 (1 cycle) of the current cycle, then the day when treatment is restarted will be counted as Day 1 of the next cycle.

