4.3.3. DLT Definition

A participant is classified as DLT-evaluable if the participant either 1) received at least 75% of the planned doses of the study intervention and have received all scheduled safety assessments during the DLT-observation period (Cycle 1 [28 days]) or 2) have experienced a DLT regardless of the percentage of planned doses received. The percentage of drug received is calculated as the percentage of the actual total amount of drug(s) administered during the DLT-observation period in relation to the planned total amount of drug(s) to be administered for the DLT-observation period. If a participant fails to meet these criteria, the participant is deemed non-evaluable for a DLT, and may be replaced. The sole exception to criterion 1 above is if the participant has missed a minority of safety assessments due to emergency situations (eg, site accessibility issues, inability to go to an external lab, etc). In such cases, the DLRM Committee may judge the participant evaluable, depending on the abundance of the available data.

For the purpose of dose escalation, all treatment-emergent AEs meeting the definition of DLT occurring in the first cycle of treatment (within 28 days of the first dose or until the participant receives the first dose of the second treatment cycle in the event of treatment delays) will be considered DLTs unless they are clearly attributable to underlying disease or intercurrent illness.

Severity of AEs will be graded according to CTCAE version 5.0. For those AEs involving a worsening of a baseline abnormality, a DLT must represent a clinically significant (in the opinion of the Investigator after discussion with the sponsor) shift from baseline.

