6. Capable of giving signed informed consent as described in [Appendix 1](#), which includes compliance with the requirements and restrictions listed in the ICD and in this protocol.

Other Inclusion Criteria:

7. ECOG PS \leq 1.
8. Life expectancy \geq 3 months.
9. Adequate hematologic function, including:
 - Absolute neutrophil count \geq 1,500/ μ L;
 - Platelet count $>$ 100,000/ μ L;

- Hemoglobin >9 g/dL.

Note: Transfusions and growth factor support to achieve inclusion are not permitted within 14 days prior to enrollment.

10. Adequate renal function, including:

- Creatinine clearance ≥ 60 mL/min calculated using the Cockcroft-Gault formula.

11. Adequate liver function, including:

- Total bilirubin $\leq 1.5 \times$ ULN unless the participant has documented Gilbert's syndrome;
- AST and ALT $\leq 1.5 \times$ ULN; ($\leq 5.0 \times$ ULN if there are liver metastases);
- Alkaline phosphatase $\leq 2.5 \times$ ULN ($\leq 5 \times$ ULN if there are bone metastases).

12. Have measurable disease per RECIST version 1.1. Lesions previously irradiated are considered measurable if progression has been demonstrated in such lesions.

13. Resolved acute effects of any prior therapy to baseline severity or CTCAE Grade ≤ 1 except for AEs not constituting a safety risk by investigator judgment.

14. Pre-treatment tumor tissue:

- All participants must provide archival FFPE tumor tissue that is of diagnostic quality and representative of their diagnosed malignancy.

- i. **Part 1:** If archival sample is older than 6 months, the participant must consent to undergo a fresh biopsy during the screening period if it can be performed safely. If a new biopsy represents a significant risk in the opinion of the investigator, the participant may be considered for enrollment, after discussion with the sponsor.
 - ii. **Part 2 and mandatory biopsy dose levels of Part 1:** Fresh tumor biopsy during screening is required unless there is archival tissues less than 3 months old and was obtained subsequent to the last systemic anti-cancer therapy and can be performed safely. If a new biopsy represents a significant risk, the participant may be considered for enrollment, after discussion with the sponsor.
15. **On-treatment biopsy:**
 - a. **Part 1:** Starting with DL3 or higher dose, participants may be asked to provide mandatory fresh pre-treatment and on-treatment biopsy. Consent for these procedures will occur during screening.

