6.1.1. Administration

6.1.1.1. PF-07265028

Participants will swallow PF-07265028 tablets whole with at least 8 ounces (240 mL) of water, and will not manipulate or chew the study intervention prior to swallowing. PF-07265028 will initially be administered QD by mouth for all cohorts on a continuous basis. Participants who are unable to swallow whole tablets may dissolve their dose in oral syringe(s) as outlined in the IP manual to allow for suspension administration either orally or via an NG tube. If supported by emerging data, BID continuous regimen may be considered. A cycle is defined as 28 days, regardless of missed doses or dose delays.

Participants will take PF-07265028 at approximately the same time within each dosing interval (ie, ± 3 hours of nominal time). On site visit days, participants will take the drug at the site after performing predose assessment. On other days, participants will be instructed to self-administer the drug at home. A dosing diary will be given to each participant to support at home dosing. The participants will be requested to note the date and time of each dose, food consumption status at the time of drug administration.

If a participant misses a dose at the scheduled time, the participant can still take the dose within 4 hours of the scheduled time. If the participant missed taking a dose after 4 hours of the scheduled time, or day of treatment, they must be instructed not to “make it up” but resume subsequent doses as prescribed. This dose will be considered as a missed dose. In addition, if a participant vomits any time after taking a dose, they should not “make it up” but to resume subsequent doses as prescribed. Lastly, if a participant inadvertently takes 1 extra dose during a day, the participant should not take the next dose of PF-07265028.

Food Requirements (Except for the Food-Effect Subset or Cohorts Evaluating Food Intake on Tolerability)

Participants will take PF-07265028 orally with at least 8 oz (240 mL) of water on an empty stomach. No food or liquids other than water will be consumed for 2 hours before and 2 hour following each dose throughout the study).

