Hematologic	Continue at the same dose level.	Continue at the same dose level.	Withhold dose until toxicity is Grade ≤ 2 , or has returned to baseline, then resume treatment at the same dose level.	Withhold dose until toxicity is Grade ≤ 2 , or has returned to baseline, then reduce the dose by 1 level and resume treatment or discontinue at the discretion of the investigator.

Specific GI toxicities potentially related to PF-07265028 should be managed according to the dose modifications described in [Table 9](#).

090177e198aafefApproved\Approved On: 22-Nov-2021 20:52 (GMT)

Table 9. Dose Modifications for PF-07265028 Related GI Toxicity

Grade 1	Grade 2	Grade 3*	Grade 4
Continue at the same dose level and, institute standard of care supportive measures at the discretion of the investigator.	Continue at the same dose level and institute standard of care supportive measures at the discretion of the investigator. If recurrent and intolerable, withhold dose until toxicity is Grade ≤ 1 , or has returned to baseline, then resume treatment at the next lower dose level	Withhold dose until toxicity is Grade ≤ 1 , or has returned to baseline, then resume treatment at the same dose level or reduce the dose by 1 level at the discretion of the investigator. If recurrent, withhold dose until toxicity is Grade ≤ 1 , or has returned to baseline, then reduce the dose by 1 level.	Withhold dose until toxicity is Grade ≤ 1 , or has returned to baseline, then reduce the dose by 1 level and resume treatment, or discontinue at the discretion of the investigator. If recurrent, permanently discontinue treatment

*Nausea, vomiting, or diarrhea must persist at Grade 3 despite optimal supportive care to require dose modification.

Note: Cycle will not be extended to cover for the missing dose.

Note: For management of GI iRAEs see [Appendix 3 Section 10.3](#).

Note: Participants with confirmed Hy's Law must be discontinued.

Table 10. Dose Modifications for PF-07265028 Related QTcF Prolongation

QTcF >480 ms \leq 500 ms	QTcF >500 ms	Recurrent QTcF >500 ms	QTcF >500 ms or >60 ms change from baseline, and Torsade de pointes or polymorphic ventricular tachycardia or signs/symptoms of serious arrhythmia

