6.1.1. Dose-Limiting Toxicities (DLTs)

- Analysis set: Per protocol analysis set.
- Analysis methodology:

For the purpose of dose escalation, the DLT observation period will be during the first cycle (28 days after the start of study treatment), or DLT window, in each participant. According to the design, cohort sizes are planned to be approximately 3, but it is required to have at least 2 DLT-evaluable patients in the dosing cohorts. The participants who cross over from Part 1A monotherapy to Part 1B combination therapy will be excluded from the DLT assessment in Part 1B.

Whether an adverse event a participant experienced during the DLT window is determined as a DLT or not is based on the DLT definitions provided in Section 4.3.3 of the protocol. A DLT yes/no checkbox will be provided in the case report form, where the investigator provides his/her judgement if an event is a DLT or not. However, the final determination will be reached between the investigators and the sponsor during the dose level review meeting (DLRM). These final decisions will be documented.

The DLT events will be summarized by dose level. A listing of the DLTs events will also be provided in which the participant primary diagnosis (malignancy), dose level the participant was enrolled to, DLT event start day and stop day relative to the cycle 1 day 1 dose date, the DLT event term, NCI CTCAE grade, relatedness to the investigational product (PF-07265028), or sasanlimab (Part 1B), outcome of the event, along with other variables deemed important, will be included.

- Missing data: All enrolled participants in Part 1 should have an indicator variable derived to be either 1 (yes) or 0 (no) based on the DLT definitions and participant's

safety data during the DLT observation window. If a participant fails to have a value on the indicator variable because the participant being non-DLT-evaluable, the participant may be replaced.

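### Restart and stopping rules conflict: haemoglobin (entry above 9, new cycle at least 10 g/dL), the consequence of a long sasanlimab hold, and QTcF re-escalation, recovery and restart dose

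*Protocol*

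**What the plan says.** **Haemoglobin.** Protocol 5.1 (criterion 9) admits participants with "Hemoglobin >9 g/dL". Protocol 6.5.4 sets a floor of 10 g/dL, with ANC and platelet floors, and says that retreatment after a toxicity interruption or "at the start of any new cycle may not occur until all of the following parameters have been met". Only the non-haematologic item in that list accepts a return to baseline. Table 8 (6.5) keeps PF-07265028 going at Grade 2 haematologic toxicity. After Grade 3 it waits for Grade 2 or lower "or has returned to baseline, then resume treatment at the same dose level". Section 6.5.3 sends the reader to 6.5.4 for the restart criteria. Table 11 (6.5.1) gives the grade boundary as "Anemia Grade ≥ 3 (hemoglobin < 8 g/dL"). Its own rule is "Resume sasanlimab at the next scheduled dose after recovery to Grade" 1 or lower, or to baseline.

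**Long sasanlimab hold.** Sections 6.5.3 and 6.5.4 set 8 weeks; beyond that, 6.5.4 ends study treatment. Table 11, for toxicity other than irAEs, allows 12 weeks for resolution and then ends sasanlimab. The irAE guidance in 10.3.5 also uses 12 weeks and ends study treatment.

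**QTcF.** Section 6.5.2 rules out any re-escalation. Table 10 allows a return to the previous level in the next cycle after QTcF above 480 and up to 500 ms. Above 500 ms, Table 10 withholds for up to 14 days, requires QTcF no more than 30 ms over baseline or under 450 ms, and cuts one level. Section 8.2.4 has its own triggers: a rise of 60 ms or more with QTcF above 450 ms, absolute QT of 500 ms or more for over 4 hours, or progressive lengthening. If QTcF rises above those thresholds during monitoring, drug is held until QTcF is back below them. It may then restart at the same dose or one level down, once discussed with the sponsor. Section 8.2.4 discontinues anyone above 515 ms or symptomatic.

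**DLT window.** Protocol 4.3.3 runs it for 28 days or "until the participant receives the first dose of the second treatment cycle in the event of treatment delays". SAP 6.1.1 says "the DLT observation period will be during the first cycle (28 days after the start of study treatment") and omits the delay clause.

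**The concern.** A site applying these sections as written can reach opposite actions for the same participant.

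The QTcF conflict is the direct safety matter. In a first-in-human trial, one section insists on fuller recovery and a lower dose, while another may allow the same dose sooner. The haemoglobin rule would withhold drug from eligible participants who have had no toxicity. The sasanlimab rules disagree on whether PF-07265028 stops as well.

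There is a smaller statistical consequence. A delayed Cycle 2 lengthens the Cycle 1 DLT window under the protocol, and Cycle 1 DLTs are the input to the dose-escalation model.

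**Working it through.** The plan states no statistical figure on this point, so there is none to reproduce. The check puts one participant through each pair of rules.

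**(a) Haemoglobin.**
- Inputs: entry above 9 (5.1); new cycle at least 10 (6.5.4); Grade 3 or worse below 8 (Table 11), so Grade 2 or lower means at least 8.
- Participant stable at 9.5: 9.5 > 9, eligible; 9.5 ≥ 8, so Tables 8 and 11 continue treatment; 9.5 < 10, so 6.5.4 bars Cycle 2. The same holds for any entry value above 9 and below 10.
- If the value does not rise within 4 weeks, the default in 6.5.4 is permanent discontinuation, unless the investigator judges otherwise after sponsor discussion.
- After Grade 3 anaemia: Table 8 restarts PF-07265028 at 8 or above, or at baseline; 6.5.4 at 10 or above. The difference is 10 − 8 = 2 g/dL. Because 6.5.3 points to 6.5.4, 6.5.4 prevails, but Table 8 does not say that it is overridden.
- The ANC (1,000) and platelet (50,000) floors in 6.5.4 equal Table 11's Grade 3 cut-offs. The haemoglobin floor is 2 g/dL above its cut-off.

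**DLT window if Cycle 2 is delayed.** SAP: 28 days. Protocol 4.3.3: 28 days plus the delay. Within the 4-week hold limit the most is 28 + 28 = 56 days. A 4-week hold starting on Day 15 gives 14 + 28 = 42 days.

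**(b) Sasanlimab.**
- If both clocks start on the same day and recovery comes at week 10: 10 > 8, so 6.5.4 ends study treatment; 10 < 12, so Table 11 lets sasanlimab resume.
- If Table 11 counts from toxicity onset and 6.5.4 from the first withheld dose, a toxicity arising just after a Q4W dose is 4 weeks old when the first dose is withheld. Then 4 + 8 = 12, and the limits coincide.
- Beyond both limits, 6.5.4 stops both drugs (Section 6 defines study intervention as both) and Table 11 stops sasanlimab alone. This difference does not depend on the clock.

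**(c) QTcF** (60 bpm, so QT equals QTcF; asymptomatic; baselines are assumed).

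| Case | Table 10 | Other section |
|---|---|---|
| Reduced after >480 to ≤500 ms, then recovered | Previous level allowed next cycle | 6.5.2: not allowed |
| Baseline 430, rises to 505 during monitoring, falls to 480 | Still withheld; needs ≤ 430 + 30 = 460, then one level lower | 8.2.4: 480 − 430 = 50 < 60, so same or next lower level after sponsor discussion |
| First value 520 | Withhold; on recovery within 14 days, restart one level lower | 8.2.4: discontinue (>515) |
| Baseline 420, 490 during monitoring (+70) | Reduce one level, keep dosing | 8.2.4: hold |

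In the second case, the rise at the peak is 505 − 430 = 75 ms, which meets the 8.2.4 trigger. That trigger clears below 430 + 60 = 490 and Table 10 at 460, a gap of 60 − 30 = 30 ms. The gap narrows when an absolute limit binds instead. With baseline 400, for example, Table 10 clears below 450 and 8.2.4 below 460, a gap of 10 ms. At QTcF 480, QT reaches 500 only when RR ≥ (500/480)³ = 1.130 s, so the second case holds above about 53 bpm.

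**The case against.** Several points on the other side are sound.

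- **Haemoglobin precedence.** A reader might infer that nothing decides between Table 8 and 6.5.4. Section 6.5.3 does decide: 6.5.4 is the restart rule. What stands is the missing baseline exception and a Table 8 row that does not mention the override.
- **8 versus 12 weeks.** A reader might infer a flat 4-week contradiction. The documents do not support that. Section 6.5.4 times time off drug and Table 11 times resolution of toxicity; no clock start is given and the two can coincide. Only the conflict over consequences is certain.
- **irAEs.** A reader might also infer that the 8-week limit cuts off participants whom 10.3.5 would let resume after a steroid taper. But 10.3.5 withholds study treatment, so PF-07265028 is off too. A taper of at least 1 month (taken as 30 days) passes the 28-day PF-07265028 limit first, and that limit can be waived after sponsor discussion.
- **QTcF.** Section 8.2.4 does not contradict Table 10 in every event. Its hold depends on QTcF rising during monitoring, and Table 10 covers only PF-07265028-related prolongation. Since 8.2.4 permits the next lower level, a cautious site could satisfy both on dose. In Part 1 Cycle 1, a Grade 3 prolongation that counts as a DLT falls under the 6.5.2 rule of resuming one level down. None of this reconciles the recovery criteria or the 515 ms rule. Table 10's own note sends readers to 8.2.4 for management, so the sections overlap. Table 10 could be an intended exception to 6.5.2, but neither says so.
- **DLT window.** A reader might infer that protocol and SAP define different windows. SAP 6.1.1 refers to protocol 4.3.3 for DLT definitions, so this is an omitted clause. Protocol 6.1.1.1 adds to the ambiguity ("A cycle is defined as 28 days, regardless of missed doses or dose delays"), but 6.5.4 counts the restart day as Day 1 of the next cycle, which agrees with 4.3.3.

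**Conclusion.** The concern holds, as conflicts in operative text that should be corrected. Four are firm:

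1. Eligible participants above 9 and below 10 g/dL cannot start Cycle 2 at their entry value.
2. Section 6.5.4 and Table 11 give different consequences for a long sasanlimab hold.
3. Section 6.5.2 forbids what Table 10 permits.
4. For an overlapping QTcF event, Table 10 and 8.2.4 differ on recovery (by up to 30 ms), on restart dose, and on values above 515 ms.

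The DLT-window wording is minor. The QTcF examples rest on assumed baselines and 60 bpm, and those involving an 8.2.4 hold also require that QTcF rose during monitoring. The 10 g/dL floor may be deliberate; the documents give no reason for it. The share of participants affected is not given, and no sample size, error rate or other stated statistical figure changes.

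**What to change.** **(a)** In 6.5.4, change the item to haemoglobin ≥10 g/dL or returned to baseline. Cross-refer Table 8's haematologic row to 6.5.4. Table 11's sasanlimab restart rule already accepts baseline and can stay. Add the 4.3.3 delay clause to SAP 6.1.1.

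**(b)** In 6.5.3, 6.5.4 and Table 11, state one limit, one clock start and one consequence (sasanlimab alone or all study treatment). Check it against the 12-week irAE rule in 10.3.5 and the 4-week PF-07265028 limit.

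**(c)** Either add to 6.5.2 an exception for what Table 10 allows, or delete the Table 10 re-escalation sentence. In 8.2.4, state three things:
- After PF-07265028-related QTcF above 500 ms, Table 10's recovery criterion and one-level reduction apply.
- Table 10's arrhythmia column (permanent discontinuation) applies whatever the QTcF value.
- If 8.2.4 triggers a hold at >480 to ≤500 ms, the hold comes before the Table 10 reduction.

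Add the discontinuation rule for QTcF >515 ms or symptoms to Table 10.

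The sponsor's clinicians should confirm which limits to keep. The cost is wording in the next protocol amendment (6.5.2, 6.5.3, 6.5.4, 8.2.4, Tables 8, 10 and 11) and one line in the SAP, with no added visits or participants.
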